5.2.5 Adaptation/Enhancement of the HOPE platform

We will assure that the indicators pertinent to the project will be captured. We will also develop a module for follow up of the cases.

5.2.6 Development of training manuals, videos and other materials for providers who will use the pocket colposcope and the thermocoagulator. These materials should be easily accessible for providers in low-resource clinics.

5.3 Implementation of the local laboratory in Cajamarca for the processing of the HPV tests.

The staff of the DIRESA laboratory will be trained in the processing of HPV tests. We will provide the necessary equipment, implement a quality control system, and set up a connection to the HOPE digital platform.

5.4 Designation of health centers to participate in the trial and training of health providers at Health Centers (intervention and control)

Providers will need to be trained about the study protocol, the national guidelines for cervical cancer, the use of the thermocoagulator, visual counseling, and pocket, and the deployment of equipment.

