Closing the gap between identification and treatment of cervical abnormalities in Lima, Perú through integraton of pocket colposcopy, telemedicine and visual counseling

Document Date: 10/10/2023

NCT05340322

Randomized Controlled Trial for the evaluation of pocket colposcopes and visual counseling for improvement in follow-up and treatment of HPV positive women in Peru: HOPE treatment trial.

I. BACKGROUND

Globally each year, there are approximately 570,000 new cases of invasive cervical cancer (CC) and 300,000 cervical cancer-related deaths. More than 90% of those deaths occur in low- and middle-income countries (LMICs)¹. The discovery of the human papilloma virus (HPV) as the etiological factor for CC has opened up several opportunities for prevention, screening, and therapy². Currently, there are HPV vaccines available (Gardasil, Gardasil 9, and Cervarix) which are prophylactic in nature and derived from adjuvanted L1-based virus-like particles of HPV, and these have proven to be very safe and efficacious in preventing cervical cancer³. However, vaccine coverage is still limited, especially in those countries with the higher burden of disease⁴. Cytology-based detection programs have failed to reduce the incidence of CC in most countries since they are complex to implement adequately, and the cytological method, the Papanicolaou (PAP), has limited sensitivity and low reproducibility. New screening strategies have appeared, especially for LMICs. Visual inspection with acetic acid (VIA) for example, uses 5% acetic acid applied to the cervix. With this procedure, the abnormal epithelium (dysplastic) turns white and can be detected with the naked eye. However, the sensitivity of VIA is similar to a Pap smear and varies among evaluators^{5,6}. Most CC cases are caused by persistent infection with high-risk human papillomavirus (hr-HPV) and disease progression from HPV infection to micro-invasive cervical cancer is typically slow (over a decade or more)^{7,8,9}. Another alternative for the screening recommended by the World Health Organization (WHO) is the detection of hr-HPV DNA starting at age 30 and regularly afterwards ever three to five years^{1,10,11}. Studies have shown that molecular HPV tests are more effective than VIA and PAP.^{12,13} Some countries, such as Australia, with wellestablished high-quality Pap smear programs have changed their programs to molecular HPV testing.

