There have been significant global efforts to ramp up screening rates to facilitate early identification of cervical cancer and its precursors. However, screening is not enough. The traditional approach for following up screen-positive woman includes a visit to a referral setting to undergo a confirmatory test which typically needs to be performed by

an expert gynecologist, who will visualize the cervix directly (VIA), or, if available, with a colposcope, which is an expensive low-power microscope. If an abnormality is found, it is biopsied and submitted for pathology. A positive diagnosis is available weeks later and requires yet another visit for treatment. Unfortunately, in LMICs, there are often not enough expert gynecologists, colposcopes, or treatment equipment, and a woman may come for the first visit, but may not necessarily understand the importance of returning for results or completing the treatment cascade. In these cases, the opportunity of saving her from cervical cancer is lost.

Recognizing these barriers, WHO has endorsed recommendations for a simple screenand-treat strategy, acknowledging that increased access to treatment with simpler protocols may result in overtreatment. In May 2018, WHO Director-General, [name], announced a call to action to eliminate cervical cancer globally¹⁴. However, unless we can ensure we have the means for accurate screening, affordable treatment, technology that does not require an expert gynecologist, and education for women that engages them in the process so that they understand the importance of completing the treatment cascade, we will not succeed in the goal of elimination.

In this study, we propose the implementation of a new low-cost technology, the Pocket Colposcope, as a tool to improve the diagnostic capabilities for cervical cancer screening and treatment of non-expert health providers in Peru, coupled with improved counseling to enhance the women's experience during the examination and to increase adherence to the completion of care.

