In recent years the global attention turned to thermal-coagulation, an electricity-powered device used for 50 years in United Kingdom and some countries in Asia; the cure rates of thermal ablation in those settings is around 90%, better than cryotherapy, and comparable to LEEP. In addition, the thermal ablation units can be powered with rechargeable batteries similar to cell phones, and very light for transportation (1 Kg) and they do not need any supplies to work. In May 2019 the WHO approved the new guidelines for use of thermal ablation, recommending thermal ablation for the treatment of pre-cancerous lesions of the uterine cervix.

II. AIMS

The continuum of care is one of the main challenges to ensure effective actions against cervical cancer. We are proposing to leverage what we are doing within the project "HOPE Peru: Women helping women fight cervical cancer" and improving treatment at the health center for those women found to be HPV(+). Our goal is to demonstrate that the combination of HPV self-sampling with the participation of community women, the Pocket colposcope and the thermocoagulator will yield a high proportion of HPV positive women who complete treatment and follow-up care.

Main Aim

To perform a demonstration trial on the feasibility of HPV self-sampling as a way to mobilize women to get to the next level of care and the feasibility of a "see and treat" strategy in a community health setting and the effectiveness of the Pocket colposcope and the thermocoagulator to improve the rates of treatment and follow up care to women who have a positive HPV results.

Specific Aims

Aim # 1: To assess the proportion of HPV positive women who go to a health center for treatment, are examined with the Pocket Colposcope and if required, received Thermocoagulation.

Aim # 2: To assess the proportion of HPV positive women that receive treatment and a 6 month follow up visit.

Aim #3: To evaluate feasibility, acceptability, and ease of use of the Pocket colposcope Aim #4: To assess the costs, cost-effectiveness, and population health impact of using the pocket Colposcope, and thermocoagulator for cervical cancer treatment.

III. LOGIC MODEL AND FRAMEWORK

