Currently, the MOH does not have a follow-up system to track and secure a successful progression of women with a positive screen test to the subsequent steps in the cervical cascade of care. This study will provide the MOH with direct insight into how cervical cancer treatment is offered in standard practice and what can be improved to facilitate the progression along the cascade with the introduction of new technology and counseling.

The cascade of care (also known as the "continuum of care") is a concept used to describe the patient's pathway within the process of receiving care for a disease²³. The most successful example of its application is within HIV care, and has also been used for TB, hepatitis C infection, other STIs, and more recently, non-communicable diseases such as diabetes. It is increasingly considered a valuable tool for scientific and public health evaluations and interventions; however, it has not been consistently applied to other conditions that might benefit from its use. As we have seen, unless we ensure that every woman at high-risk for cervical cancer, and every woman found to be HPV (+) receives the care she needs, investments in screening are largely lost.

Framework

a. "The Continuum of Care" construct

The construct of the continuum of care derives from the models used in the 1980s and 1990s to understand systems of care within STI and TB. However, only in 2014 did it become more popular in public health research and program evaluation due to its effectiveness in identification of gaps within HIV care and in proposing global goals for controlling the HIV epidemic. Its usefulness mainly lies on the visual representation of the model as a bar graph where eat bar represents the proportion of persons completing each step along the continuum of care of a disease (prevention, diagnosis, linkage to treatment, adherence to treatment or retention, and successful treatment). This bar graph thus helps to identify the losses occurring at each step of the continuum of care²³. The use of continuum models that reflect longitudinal rather than cross-sectional data may be particularly important for understanding chronic conditions.

The specificities of the continuum, such as the starting point, the endpoint, the steps being considered, or the denominators used for each step, are not clearly defined, and usually vary according to the disease or condition being studied.

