4.1 Study Design

This is a demonstration/implementation trial.

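### The title, the 5.4 heading, 5.5 and the timeline imply a randomized or controlled trial, but the aims, sample size and analysis describe a single group, and no allocation method exists

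*Combined protocol and SAP*

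**What the plan says.** **Text that states or presupposes randomization or controls.**
- The title reads "Randomized Controlled Trial for the evaluation of pocket colposcopes and visual counseling".
- The timeline (section VII) uses the abbreviation RCT in its approvals row and gives controls their own entry in the training row.
- The heading of 5.4 provides for "training of health providers at Health Centers (intervention and control").
- Section 5.5 reserves visual counseling training for HOPE Ladies in intervention areas.

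**Text that describes one group.**
- Section 4.1: "This is a demonstration/implementation trial". The Main Aim and 5.7 also call it a demonstration trial.
- Section 4.3 derives one pool of 800 HPV-positive women, gives a precision for two primary proportions, and says historical data will be sought for comparison.
- Section 4.6 allocates HPV-positive women to centers by geography.
- Section 5.7 plans descriptive analysis, with historical comparison if suitable data exist.
- The 5.9 metrics table plans 10-12 Pocket Colposcopes; 4.3 and the timeline give 10-12 centers in all.

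**What is being evaluated.** The Background proposes the device "coupled with improved counseling to enhance" the woman's experience, and section III speaks of improving the cascade "with the introduction of new technology and counseling". The goal in section II lists only "the combination of HPV self-sampling with the participation of community women, the Pocket colposcope and the thermocoagulator". The Main Aim refers to "the effectiveness of the Pocket colposcope and the thermocoagulator to improve the rates of treatment and follow up care". The 5.4 body gives one list of provider training topics, including "the use of the thermocoagulator, visual counseling, and pocket, and the deployment of equipment".

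**The concern.** The plan claims a property, randomization with controls, that its methods do not contain. A reader of the title would expect a between-arm estimate of what the devices add; the analysis section cannot produce one. The Main Aim's effectiveness wording raises the same expectation.

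There is a practical side as well. Because the intervention areas are not defined, whoever trains the HOPE Ladies cannot tell which of them should learn visual counseling. Counseling is in the title, the Background and section III but not in the section II goal, so the content of the package is itself unclear. Provider training may also differ between 5.4 and the timeline.

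**Working it through.** **1. Which design does the sample size fit?** Inputs from 4.3: 10,000 tested, 10% positive, 80% uptake. The 95% level and p = 0.5 are assumptions, since 4.3 states neither.

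n = 10,000 × 0.10 × 0.80 = 800

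Half-width = 1.96 × √(0.5 × 0.5 / 800) = 3.46%

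This reproduces the stated 3.5% or better, as one undivided group with no design effect. The center figures agree: 10 × 60 = 600 to 12 × 80 = 960 women, a range that contains 800 and uses every center as one pool.

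Under an assumed 1:1 split (400 per arm), the half-width for a difference would be 1.96 × √(2 × 0.25 / 400) = 6.9 points before clustering, so 3.5% would not carry over to a two-arm design.

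**2. Is there an allocation procedure?** A search of sections 4.1 to 5.9 finds only the geographic assignment in 4.6. That argues against randomizing individual women; on its own it would not exclude allocating centers. No unit, method, ratio, number of control centers or between-arm comparison is given.

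**3. Devices.** 10-12 colposcopes against 10-12 centers suggests one each, leaving no center without the device. This is inferred from matching ranges; the protocol does not say it.

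**4. Training.** The 5.4 body, under a heading that names both center types, lists visual counseling and the Pocket Colposcope. The timeline row appears to give controls a package printed as IV/A plus thermocoagulator, and intervention centers the Pocket Colposcope plus thermocoagulation.

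**5. HPV-positive counts.** Timeline: 2,400 / 10,000 = 24%. Section 4.3: about 1,000 / 10,000 = 10%. At the same 80% uptake, 2,400 × 0.80 = 1,920 women; 1,920 / 12 = 160 and 1,920 / 10 = 192 per center, against 60-80 in 4.3.

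**6. Precision with clustering.** Section 4.3 cites a sample size method for cluster-randomized trials (reference 27) but states no ICC or design effect. Take DE = 1 + (m − 1) × ICC, with m = 800/12 ≈ 67 or 800/10 = 80, and half-width = 1.96 × √(p(1 − p) × DE / 800). The ICC values are assumed.

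| m | ICC | DE | Effective n (800/DE) | Half-width, p = 0.5 |
|---|---|---|---|---|
| 67 | 0.01 | 1.66 | 482 | 4.46% |
| 80 | 0.01 | 1.79 | 447 | 4.64% |
| 67 | 0.05 | 4.30 | 186 | 7.18% |
| 80 | 0.05 | 4.95 | 162 | 7.71% |

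At p = 0.8 the unclustered half-width is 2.77%. With ICC 0.01 it is 2.77 × √1.66 = 3.6% to 2.77 × √1.79 = 3.7%. With ICC 0.05 it is 2.77 × √4.30 = 5.7% to 2.77 × √4.95 = 6.2%.

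**The case against.** The strongest reply is that the aims, the design section, the sample size and the analysis all lean the same way, and that the conflicting words sit in the title, one heading, one clause of 5.5 and a few timeline rows. They may be left over from a different study plan; the title page names Lima while 4.2 names Cajamarca. That is plausible, but the documents do not say so, and leftover wording that still assigns training by area needs correcting either way.

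Several stronger readings are tempting and are not supported:

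- **A randomized trial whose methods were left out.** A reader might infer this from the title. Sections 4.1, 4.3, 4.6 and 5.7 point away from it, and nothing commits the sponsor to reporting a randomized or causal result.
- **Training instructions that certainly contradict each other.** The 5.4 body can be read as a combined list across center types, without every provider receiving every item. The opposing timeline row is damaged in extraction. The conflict is likely, not certain.
- **Centers left without a workload figure.** Section 4.3 gives 60-80 women each; the 2,400 appears only as a timeline milestone.
- **A precision figure that is simply wrong.** It is correct at p = 0.5 for independent women. The plan hopes for high proportions, where the interval is narrower: at p = 0.9 and ICC 0.01 it is 1.96 × √(0.09 / 800) = 2.08%, times √1.66 to √1.79, or 2.7% to 2.8%. If uptake means attendance, the Aim 1 denominator is nearer 1,000, giving 1.96 × √(0.25 / 1,000) = 3.1% unclustered.

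It is also fair to say that the precision and count issues are separate from the design label. They would arise in a correctly labeled single-group study.

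**Conclusion.** The contradiction over design is real and should be fixed. The text as a whole points to a single-group demonstration study carrying a randomized label. On that reading the primary proportions do not change; what changes is the claim. The study can estimate how many women complete treatment and follow-up under the package. It cannot attribute an improvement to the devices. The only historical rate given, about 30%, comes from Callao in 2014 and from women with abnormal high-grade PAP results, so it is not a like-for-like comparator.

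The undefined intervention areas are a definite gap. The difference in provider training is probable only, and one device per center is an inference.

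Two separate points stand. The HPV-positive counts differ by a factor of 2.4 (2,400 / 1,000). The precision of 3.5% rests on no clustering by center at p = 0.5; allowing for it gives about 4.5% to 7.7% under an assumed ICC of 0.01 to 0.05, and less at high proportions. The documents give no ICC, so that range shows sensitivity and is not an estimate.

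**What to change.** The sponsor should state which design is intended and reconcile the title, section II, 4.1, 4.3, 4.6, 5.4, 5.5, 5.7, 5.9 and the timeline with it.

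**If single-group:**
1. Remove the randomized, RCT, control and intervention-area wording.
2. State one training package and who receives visual counseling, consistently from the title through 5.5.
3. Word the Main Aim as estimating proportions under the package, and label any historical comparison descriptive and non-causal.

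**If a control arm is intended:** define the allocation unit, method and ratio, the areas, the device distribution and the training by arm. Add a cluster-adjusted between-arm analysis and a matching sample size in place of the 3.5%.

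**In either case:** align the timeline's 2,400 with the roughly 1,000 and the 60-80 per center in 4.3.

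**For the single-group precision:** state that 3.5% assumes p = 0.5 and no clustering by center, or give a cluster-adjusted figure with its assumed ICC.

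For a single group the cost is wording and one precision statement, with no added women, visits or centers. The downside is giving up the randomized label and accepting a less favorable precision. A two-arm design costs more: a new sample size, an allocation procedure and an analysis resting on only 10-12 centers.

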5.5 Identification and recruitment of women leaders (HOPE Ladies)

Through key informants, data will be collected on groups and activities of women in the community that will allow us to identify potential female "leaders". The field coordinator will meet in different places (mothers clubs, wawawasi, health center, municipality, etc.) with these women and they will be introduced to the HOPE model and invited to participate. The leaders will receive training specifically on cervical cancer, HPV testing, importance of treatment and for those HOPE ladies in the intervention areas they will learn about the visual counseling. As per the HOPE model, the HOPE Ladies will receive a small incentive (around \$1) for each HPV test process from a woman they contacted.

We hope to recruit between 2-4 HOPE Ladies per catchment area of a health center with approximately 24-48 women leaders in total among the 10-12 health centers. We will assess knowledge and address myths about cervical cancer, and we will build strategies to improve the coverage in the community. We will use the materials, contents, and methodology that we have already developed, piloted, and used to train and coach the HOPE Ladies.

5.6 Initiation of the trial, distribution of collection kits to HOPE Ladies, collection of data, and visits to health centers by local monitors

5.7 Data collection and analysis

For the demonstration trial we will collect process information about the distribution of HPV tests and basic information from women who participate in the HPV self-sampling as age, history of previous paps. For the HPV (+) women coming to the centers we will collect data on dates, procedures and results of procedures performed (pocket colposcopy, thermocoagulation, other procedures as leep/hysterectomy). To maintain the confidentiality of the information, we will use codes and keep protected health information separate from the rest of the study data. At the end of the study, personal identifiers will be destroyed. The data will be stored in a specially developed database. The information from the source documents will be reviewed and encrypted. We will use descriptive analysis of the data (process and outcomes) and comparisons with historical information if available and appropriate.

Activity	KPI Metric	How to measure metric
Conduct a baseline KAP survey of a sample of providers regarding HPV tests and cervical cancer management	Survey performed	Report of survey results
Conduct a baseline assessment of health centers	Assessment performed	Report of assessment

5.9 Process and Impact Measures

in the Andean Region where we will be working		
Implementation of local laboratory with capabilities to process HPV testing	1 laboratory implemented for HPV testing	Visit Report
Identification of rural health clinics in Andean region of Peru and provision of appropriate equipment (pocket colposcope, thermocoagulators)	 # of health clinics (10-12) # of innovations deployed # thermocoagulators deployed (#10-12) # pocket colposcopes deployed (10-12) 	Visit reports
Send staff to train HOPE Ladies in the rural regions chosen	# HOPE Ladies trained and registered	HOPE informatics platform
Preparation of tools for the use of pocket colposcope and thermocoagulator	manual of use of pocket colposcope and thermocoagulator finished in Spanish. Video tutorial for the use of pocket colposcope	Reports Tools ready
Send staff to train health providers in the use of pocket colposcope and thermocoagulators	 # of health providers trained on the use of pocket colposcope # of health providers using pocket colposcope # of providers using thermocoagulator 	Reports
Provide 10,000 HPV self- sampling kits for HOPE ladies to distribute	 # of HPV tests distributed to HOPE ladies # of HPV tests correctly returned # of HPV tests processed # of HPV tests positive # of women who receive HPV positive results 	HOPE informatics platform

Facilitate women HPV (+) to get treatment at Health centers	% of HPV (+) women coming to the health center for treatment	Monitors/hope ladies HOPE informatics platform
Health centers giving treatment and F/U to HPV (+) women	-% of HPV (+) women completing treatment -% of HPV (+) women completing F/U at 6m	Monitors/ review health centers records (check list) HOPE informatics platform
Conduct a post-study evaluation (qualitative, quantitative) of providers to evaluate acceptability and ease of use (pocket colposcope)	# of providers who indicate they would use the Pocket/thermocoagulator regularly for cervical cancer diagnosis/treatment or found it useful	Report of results
Measuring Efficiency	-Average time to come for treatment -Average time to complete treatment	Monitors/ review health centers records (check list) HOPE informatics platform
Cost-effectiveness	Complete cost of care cascade Patient level cost Monthly budget Cash on hand Co-funder contribution Personel	Report

*PC + TC = Pocket Colposcopy + Thermocoagulator

VI. ETHICAL CONSIDERATIONS

The study will be presented for IRB approval by Cayetano Heredia University and Duke University.

VII. TIMELINE

Timeline		Year 1									Year 2													
	М1	M2	М3	м4	M5	M6	М7	M8	м9	M10	м11	M12	М1	M2	МЗ	м4	M5	M6	М7	M8	мэ	м10	M11	M12
	AGO	SEP	OCT	NOV	DEC	JAN	FEB	MAR	APR	MAY	JUN	JULY	AGO	SEP	OCT	NOV	DEC	JAN	FEB	MAR	APR	MAY	JUN	JULY
Prepare all the docs for IRB, and obtain approvals	\mathbf{X}	X																					i d	
Send docs for RCT and Obtain approval from National Institute of Health for the use of Pocket																								1
colposcope in trial and facilitate shipment to Peru																								1
Initial coordinations with Regional government/approvals		X	X																					-
Hiring/training team		X																						1
Identify and visit 10-12 health centers in Andean Region to be included in the trial		X	X	X																				1
Conduct baseline data collection in each center (2 days observation workflows, costing)																							i I	1
Interview personnel about barriers for cervical cancer screening, potential solutions etc																								1
Procurement of additional supplies/materials/equipment missing at health centers for see/and																								1
treat																								1
																								1
Integration of mhealth software platform with HOPE platform																								1
																								1
Procurement of thermocoagulators																							i I	1
Shipment of pocket colposcopes to Peru (needed to start the training)						X										1								1
			_		_																			1
Prepare/Print educational materials for IVA. Pocket colposcope, thermocoagulator.			X																					1
Training and implementation of health contents: Controls IV/A/thermocoagulator Intervention																								1
Pocket colooscone/thermocoagulation/ethical issues consents etc						\mathbf{X}	X																i I	1
Procurement of HPV equipment																								(
Procurement of HPV tests (10 000 total, but we have to buy it in batches)									-															(
									-															
Identification and training of women from the community (HOPE Ladies) who will promote and					\mathbf{X}	\mathbf{X}	X																	1
distribute HPV testing			_	_	_	_		_	_		_	_	_	_	_	_		_	_	_	_	_	_	
Periodic meetings/communications with authorities MOH (including report of final findings)					N N	N N					× ×		×							×		×		
HOPE Ladies start promotion and distribution of HPV self-sampling							X	_																
